At the unit, the investigator should assess and determine whether the subject is at risk to develop ketoacidosis or is progressing towards ketoacidosis based on the subject's medical history, physical examination, and supportive laboratory results. The investigator should then determine whether the subject can be treated at the unit or should be referred to the local hospital for further evaluation and treatment of DKA.

The diagnosis of DKA will be made if the following are seen:

- Plasma glucose > 250 mg/dL (> 13.9 mmol/L)
- Increased anion gap metabolic acidosis (> 10 - 12 mEq/l) associated with pH < 7.30 and bicarbonate level < 18 mEq/l
- Elevated plasma ketone levels (> 3.0 mmol/L)

The diagnosis of eDKA will be made if the subject has the following:

- Increased anion gap metabolic acidosis as outlined above
- Elevated plasma ketones with plasma glucose < 250 mg/mL

However, any subject with a pH of < 7.35 associated with ketones > 3.0 mmol/L (regardless of glucose levels) may be considered to be progressing towards ketoacidosis. Therefore, such subjects should be discontinued from the study (Section 4.1.6) and monitored closely per local protocols.

Any event of DKA or eDKA should be managed according to standard local protocols.

In reporting DKA events, it is important to distinguish ketosis from DKA. Low levels of ketosis, in which blood or urine ketone values are elevated, can occur in individuals who follow a low-carbohydrate, high-fat diet or after prolonged periods of fasting. Ketosis is a

benign condition if symptoms are absent and the blood pH remains within normal limits (ie, no acidosis). In contrast, a DKA episode may be confirmed when a subject has potential symptoms of DKA as described above, elevated blood/urine ketone values, metabolic acidosis (characterized by low arterial blood pH, decreased serum bicarbonate, and an increased anion gap), and hyperglycemia (although some individuals may have normal or only mildly elevated blood glucose levels).

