 - ALT and/or AST are $8 \times$ ULN

If a subject is required to or chooses to discontinue the investigational product, every reasonable effort should be made for the subject to remain in the study for follow up and to complete all other study procedures until the scheduled end of the study. It is important that

investigators and site staff familiarize themselves with procedures for maintaining such subjects in the study to collect their data as scheduled. Subjects who are permanently discontinued from receiving investigational product will be followed for protocol-specified assessments including follow-up of any AEs unless consent is withdrawn specifically from further study participation (Section 4.1.5), the subject is lost to follow-up, the subject starts alternative treatment, or the subject is enrolled in another clinical study.

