Table 4.2.3-1 Schedule of Treatment Period Procedures

Study Period	Treatment period											
	100 µg			200 µg			300 µg					
Visit Number	V4			V5	V6	V7	V8	V9	V10	V11		
Procedure/ Study Day	-2	-1	1	2	7	8	14	15	22	27	28	29
Inpatient or Outpatient	Inpatient			Outpatient	Outpatient	Outpatient	Outpatient	Outpatient	Outpatient	Inpatient		
Dapagliflozin PK ⁿ		X	X		X	X	X	X			X	X
Ketones PK ^{o, r}		X	X		X	X	X	X			X	X
█████			█									█
MMTT sampling for glucose, c-peptide, glucagon, insulin, active GLP-1 ^q		X									X	
FFA (fasting)		X			X		X				X	
HbA1c	X										X	
FPG		X			X		X				X	
Collect urine for:												
Urinalysis	X						X		X	X		
Pregnancy test	X						X		X	X		
24-hour urinary glucose ^s			X								X	

Table 4.2.3-1 Schedule of Treatment Period Procedures

Study Period	Treatment period											
MEDI0382 Dose level	100 µg			200 µg		300 µg						
Visit Number	V4		V5	V6	V7	V8	V9	V10	V11			
Procedure/ Study Day	-2	-1	1	2	7	8	14	15	22	27	28	29
Inpatient or Outpatient	Inpatient		Outpatient	Outpatient	Outpatient	Outpatient	Outpatient	Outpatient	Outpatient	Inpatient		
Drug and alcohol screen ^t	X									X		
Staff review of daily ketone testing data	X				X		X		X	X		
Subjects finger-prick testing of ketones using test strips ^u	←-----For the duration of the study until 14 ± 2 days after last dose-----→											
CGM ^v	←-----From Day -1 until 28 ± 4 days after last dose -----→											
CGM sensor application/change ^w		X					X				X	
Assessment of AEs/SAEs	←-----For the duration of the study-----→											
Concomitant medications	←-----For the duration of the study-----→											

ABPM = ambulatory blood pressure monitoring; ██████████ AEs = adverse events; BP = blood pressure; CGM = continuous glucose monitoring; ECG = electrocardiogram; FFA = free fatty acid; FPG = fasting plasma glucose; GLP-1 = Glucagon-like peptide-1; HbA1c = hemoglobin A1c; HR = heart rate; IP = investigational product; MMTT = mixed meal tolerance test; PK = pharmacokinetics; RR = respiratory rate; SAEs = serious adverse events; SC = subcutaneous(ly); V = visit

- ^a The eligibility check should be based on all clinical measurements and blood tests taken during the screening visit (V1) with the exception of vital signs, urinary illicit drug, and pregnancy tests, which should be rechecked on Day -2. An abbreviated physical examination and repeat medical history should also be undertaken on Day -2 to ensure the subject is well enough to commence dosing.

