4.2.4 Follow-up Period

Table 4.2.4-1 shows all procedures to be conducted during the follow-up period.

After the end of the follow-up period, subjects will return to the care of their own physicians according to local requirements and local standards.

Table 4.2.4-1 Schedule of Follow-up Procedures

Study Period	Follow-up Period	
Visit Number	V12	End-of-Study Visit V13
Procedure/Study Day	14 days post last dose (± 2 days)	28 days post last dose (± 4 days)
Physical examination (abbreviated)	X	X
Body weight		X
ECG		X
Vital signs (HR, BP, RR, temperature)	X	X
Serum chemistry		X
Calcitonin		X
Hematology		X
Urinalysis		X
		
Assessment of AEs/SAEs	X	X
Concomitant medications	X	X
Staff review of daily finger-prick ketone testing data	X	
CGM sensor change	X	
Remove CGM sensor		X

 AE = adverse event; BP = blood pressure CGM = continuous glucose monitoring; ECG = electrocardiogram; EOS = end of study visit; HR = heart rate; RR = respiratory rate; SAE = serious adverse event; V = visit

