4.8.4 Safety

4.8.4.1 Analysis of Adverse Events

Safety analysis will be based on the As-treated population. Adverse event collection begins after the subject signs the ICF and lasts until the end of the study. Treatment-emergent AEs

(TEAEs) and treatment-emergent SAEs (TESAEs) will be coded by the most updated version of the Medical Dictionary for Regulatory Activities (MedDRA), and the type, incidence, severity and relationship to investigational product will be summarized by MedDRA's System Organ Class, Preferred Term, and by treatment group. Treatment-emergent AEs leading to discontinuation, TEAEs leading to death, and deaths will also be summarized. Specific TEAEs will be counted once for each subject for the calculation of percentages. In addition, if the same TEAE occurs multiple times within a particular subject, the highest severity and level of relationship observed will be reported.

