5.4.1 Time Period for Collection of Adverse Events

All AEs and SAEs will be collected from the time of admission to the clinical unit (Day -2) throughout the treatment period and including the follow-up period (28 ±4 days after the last dose of investigational product (inpatient Visit 13).

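### Protocol 4.1.6 ends firm follow-up when a subject off product starts undefined alternative treatment or joins another study, and 1.6.4 takes ketoacidosis cases off study: a minor, cheap wording fix

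*Protocol*

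**What the plan says.** The closing paragraph of protocol section 4.1.6 makes two statements about subjects who stop investigational product. The first is a retention rule without exceptions: "every reasonable effort should be made for the subject to remain in the study for follow up", with the remaining study procedures completed up to the scheduled end. The second is a firm duty to follow permanently discontinued subjects for the assessments in the protocol, AEs included. That duty falls away if consent is withdrawn, or if "the subject is lost to follow-up, the subject starts alternative treatment, or the subject is enrolled in another clinical study". Neither the protocol nor the SAP says what counts as alternative treatment.

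The sections on AE collection give the general window. Section 5.4.1 collects AEs "throughout the treatment period and including the follow-up period (28 ±4 days after the last dose of investigational product". Section 4.8.4.1 says: "Adverse event collection begins after the subject signs the ICF and lasts until the end of the study". (They differ on when collection starts, which is not at issue here.) Table 4.2.3-1 carries the row "Assessment of AEs/SAEs" for the duration of the study. Table 4.2.4-1 repeats the assessment at V12 and at V13, the latter timed at "28 days post last dose (± 4 days".

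Section 1.6.4 treats a pH below 7.35 with ketones above 3.0 mmol/L as possible progression to ketoacidosis and says "such subjects should be discontinued from the study (Section 4.1.6) and monitored closely per local protocols". Item 6 of section 4.1.6, which covers the same event, is a reason to give no more investigational product. It does not say that the subject leaves the study.

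**The concern.** Safety and tolerability is a secondary objective, and ketoacidosis is one of the potential risks named in section 1.6. Follow-up matters most for subjects who stop product for a safety reason. Some of them may then need a new glucose-lowering drug, and on the wording of 4.1.6 that start releases the site from the firm follow-up duty. Because the term is undefined, sites may also apply it differently: one may count any new antidiabetic drug, another only a lasting replacement. Section 1.6.4 raises a similar problem for subjects progressing to ketoacidosis, since a site that reads it literally ends study participation where 4.1.6 asks for retention. In both cases the data lost would come from subjects selected by how they fared on treatment, so the loss could be informative.

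**Working it through.** **1. The plan's own figure.** Protocol 4.8.2 states power above 95% with 23 per arm at two-sided alpha 5%. The standardized effect is 30/20 = 225/150 = 1.5. Normal approximation: 1.5 × √(23/2) − 1.960 = 5.087 − 1.960 = 3.127, which gives 99.9%. A noncentral t calculation also gives 99.9%, so the statement is reproduced. A switch before Day 28 could also cost the Day 28 meal test, and SAP 3.4.1.2 does not impute it. The documents give no dropout rate. For assumed numbers remaining per arm, t-based power is 99.6% at 20, 99.2% at 18, 96.8% at 14 and 93.9% at 12. Power is not the issue.

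**2. The rules side by side.**

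| Section | Rule | Exceptions stated |
|---|---|---|
| 4.1.6, retention sentence | Keep the subject to the scheduled end | None |
| 4.1.6, follow-up sentence | Assessments and AE follow-up after stopping product | Consent withdrawn, lost, alternative treatment, another study |
| 5.4.1 | AEs to 28 ± 4 days after last dose | None |
| 4.8.4.1 | AEs to end of study | None |
| Table 4.2.4-1 | AE assessment at V12 and V13 | None |
| 6.3 | Non-completers | Only consent withdrawn or lost |

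**3. Which exceptions are avoidable.** After withdrawal of consent, 4.1.5 stops data collection. After loss to follow-up, collection is impossible. For another study, 4.1.3 item 4 prohibits concurrent participation, which explains ending the visits. Starting another drug blocks nothing. Section 4.7 already requires medication up to the end-of-study visit to be reported and recorded in the eCRF. Alternative treatment is therefore the clearly avoidable reason.

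**4. How the clause could be reached.** Under 4.1.6 item 6, confirmed ketoacidosis ends dapagliflozin for good. Item 8 covers renal decline that rules out metformin. Replacement therapy is a plausible next step in either case, but this is an inference: neither item says that a replacement is started. Both triggers should be rare, because 1.6.4 rates the ketoacidosis risk as very low and 4.1.3 excludes a history of ketoacidosis and eGFR of 60 or below.

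**5. What is exposed per affected subject.** The post-dose AE window is 28 − 4 = 24 to 28 + 4 = 32 days. The subject can lose at most what remains of it, including V12 (12 to 16 days after the last dose) and V13, and daily ketone testing to 14 ± 2 days. Scheduled treatment-period assessments after the switch are also exposed.

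**6. Effect on the safety tables.** Section 4.8.4.1 says "Specific TEAEs will be counted once for each subject for the calculation of percentages". An event recorded before the switch therefore stays in the incidence. Only a subject whose sole occurrence falls after the switch is missed. With 23 per arm, k such subjects lower that arm's incidence of the event by k/23: 1/23 = 4.3, 2/23 = 8.7 and 3/23 = 13.0 percentage points. The values k = 1 to 3 are assumed. If sites keep collecting under 5.4.1, the loss is zero.

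**The case against.** A reader might infer that 4.1.6 flatly contradicts 5.4.1, or forbids AE collection after a switch. The documents do not support that. Sections 5.4.1 and 4.8.4.1 and the schedules also omit withdrawal of consent and loss to follow-up, and nobody would read them as overriding those. They can be taken as the general window, with 4.1.6 as the specific rule for subjects off product. In addition, 4.1.6 lifts a duty without imposing a ban, and its retention sentence still applies.

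A reader might also infer that serious events would go unrecorded. Section 5.5 requires any SAE during the study to be reported within 24 hours of the site's becoming aware of it, whether or not it is related to product. Section 5.4.2 covers unresolved events, and Appendix 10.5 covers potential Hy's law cases. The early discontinuation visit in 4.2.4.1 includes AE/SAE assessment, ECG, vital signs and laboratory tests, so events up to exit are captured.

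Further, 4.3 points per missed subject is true of any 23-subject arm and is not an estimate for this trial. AEs after a switch may be confounded by the new drug. The sentence in 1.6.4 sits in the benefit-risk text, requires close monitoring, and points to a section whose operative rule is clear.

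All of this stands and keeps the point small. Three things remain. One stopping reason is undefined and unnecessary. The exit visit sees nothing that happens after exit, and 5.5 depends on the site learning of an event. The wording of 1.6.4 also differs from the rule it cites.

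**Conclusion.** The point holds as a minor improvement to the wording. Followed literally, 4.1.6 and 1.6.4 allow a site to drop scheduled assessments and miss new, mainly non-serious, AEs in a few subjects, some of whom stopped for a safety reason. Section 1.6.4 concerns study retention and data; clinical care is covered by the monitoring it requires. The number affected cannot be derived, because the documents give no discontinuation or rescue rate; that it is probably small is a judgement from the rarity of the triggers. No stated figure changes, and the direction of any bias is not shown. The conclusion assumes that sites act on the exception in 4.1.6 or the literal text of 1.6.4 rather than on the retention sentence and 5.4.1.

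**What to change.** 1. In 4.1.6, delete the start of alternative treatment as a reason to end follow-up. State that scheduled assessments and AE/SAE collection through 28 ± 4 days after the last dose, including V12 and V13, continue unless consent is withdrawn or the subject is lost to follow-up, and that the new treatment is recorded as a concomitant medication.
2. In 1.6.4, say that the subject is discontinued from investigational product instead of from the study.
3. Optional: for subjects who enter another study, keep AE contact by telephone to the end of the same window. Section 6.3 already recognises telephone contact as an assessment. Full visits need not be asked for, given the ban on concurrent participation.

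The cost is wording in two sections of an amendment and a few visits for early stoppers that the schedule already contains. Events after the switch may be confounded by the new drug, which the concomitant-medication record would help to interpret. The sample size is unaffected.

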4.1.7 Replacement of Subjects

Subjects who withdraw from the study may be replaced where possible.

4.1.8 Withdrawal of Informed Consent for Data and Biological Samples

Biological Samples Obtained for the Main Study

Study data are protected by the use of a SID number, which is a number specific to the subject. The investigator is in control of the information that is needed to connect a study sample to a subject. A subject's consent to the use of data does not have a specific expiration date, but the subject may withdraw consent at any time by notifying the investigator. If consent is withdrawn, any samples collected prior to that time may still be given to and used by the sponsor but no new data or samples will be collected unless specifically required to monitor safety of the subject.

If a subject withdraws consent to the use of donated biological samples, the samples will be disposed of/destroyed and the action documented. If samples are already analyzed, MedImmune is not obliged to destroy the results of this research (Appendix 10.6).

4.2 Schedule of Study Procedures

Whenever vital signs, 12-lead ECGs, and blood draws are scheduled for the same nominal time, the assessments should occur in the following order: 12-lead ECG, vital signs, and then blood draws. The timing of the first 2 assessments should be such that it allows the blood draw (eg, PK blood sample) to occur at the exact nominal time.

4.2.1 Enrollment/Screening Period

Table 4.2.1-1 shows all procedures to be conducted at the screening visit. Assessments should be performed in the order shown in the table.

Table 4.2.1-1 Schedule of Screening Period Procedures

Study Period	Screening
Visit Number	V1
Procedure/Study Day	Day -89 to Day -29
Written informed consent/ assignment of SID number	X
Medical history (including smoking and alcohol history)	X
Concomitant medications	X
Physical examination (full)	X
Body weight, height, and BMI calculations	X
12-lead digital ECG	X
Vital signs (HR, BP, body temperature, and RR)	X
Collect blood for:	
Serum chemistry (including eGFR calculation)	X
Hematology	X
Calcitonin	X
HbA1c	X
Coagulation parameters	X
Hepatitis B and hepatitis C serology; HIV-1 and HIV-2 antibodies	X
Serum pregnancy test (β -hCG, female subjects only)	X
Collect urine for:	
Urinalysis (dipstick)	X
Drug and alcohol screen ^a	X
Check willingness and ability to self-administer IP ^b	X
Verify eligibility criteria	X

β -hCG = beta human chorionic gonadotropin; BMI = body mass index; BP = blood pressure; ECG = electrocardiogram; eGFR = estimated glomerular filtration rate; HbA1c = hemoglobin A1c; HIV = human immunodeficiency virus; HR = heart rate; IP = investigational product; RR = respiratory rate; SID = subject identification; V = visit.

^a Breath alcohol testing is acceptable as an alternative to urine testing.

^b Subject's ability to self-administer investigational product will be verified using normal saline SC injections.

4.2.2 Run-in Period

Table 4.2.2-1 shows all procedures to be conducted at the run-in period visits for subjects on metformin monotherapy only.

Table 4.2.2-1 Schedule of Run-in Period Procedures

Study Period	Run-in	
	V2	V3
Visit Number	Day -28	Day -14
Procedure/Study Day		
Verify eligibility criteria	X	
Medical history (including smoking and alcohol history)	X	
Abbreviated physical examination	X	X
Concomitant medications	X	
Body weight	X	
12-lead digital ECG	X	
Vital signs	X	X
Collect blood for:		
Serum chemistry (predose) ^a	X	X
Hematology (predose) ^a	X	X
HbA1C (predose) ^a	X	
Amylase, lipase and lactate (predose) ^a	X	X
PK for dapagliflozin	X	
Collect urine for:		
Urinalysis (dipstick)	X	
Drug and alcohol screen ^b	X	
β-hCG (pregnancy test)	X	X
Assessment of AEs/SAEs	X	X
Diet and lifestyle counselling	X	X
Discharge from unit	X	X
Subject administration of oral dapagliflozin 10 mg	X	X
Training of subject on glucose and ketone monitoring	X	
Subject finger-prick testing of ketones using test strips		X

AE = adverse event; ECG = electrocardiogram; β-hCG = beta human chorionic gonadotropin; HbA1c = hemoglobin A1c; PK = pharmacokinetics; SAE = serious adverse event; V = Visit

^a Blood collection is predose on Day -14 only.

^b Breath alcohol testing is acceptable as an alternative to urine testing.

4.2.3 Randomized Treatment Period

Table 4.2.3-1 shows all procedures to be conducted from inpatient Visit 4 (Day -2 to Day 1) until the end of the treatment period (inpatient Visit 11, Day 27 to Day 29). Assessments should be performed in the order shown in the table.

Whenever vital signs, 12-lead ECGs, and blood draws are scheduled for the same nominal time, the assessments should occur in the following order: 12-lead ECG, vital signs, and then

blood draws. The timing of the first 2 assessments should be such that it allows the blood draw (eg, PK blood sample) to occur at the exact nominal time.

Table 4.2.3-1 Schedule of Treatment Period Procedures

Study Period	Treatment period											
MEDI0382 Dose level	100 µg			200 µg			300 µg					
Visit Number	V4			V5	V6	V7	V8	V9	V10	V11		
Procedure/ Study Day	-2	-1	1	2	7	8	14	15	22	27	28	29
Inpatient or Outpatient	Inpatient			Outpatient	Outpatient	Outpatient	Outpatient	Outpatient	Outpatient	Inpatient		
Verify eligibility criteria ^a		X										
Admit to clinic	X									X		
Discharge home ^b		X	X									X
Medical and disease history	X											
Physical examination (abbreviated)	X				X		X		X	X		
Body weight ^c			X									X
12-lead digital ECG ^d			X		X		X		X	X		
Vital signs ^e	X		X		X	X	X	X	X		X	X
24-hour ABPM ^f	X						X				X	
Randomization ^g		X	X									
SC injection training ^h	X	X										
Administration of dapagliflozin ⁱ	←-----For the duration of the study-----→											
Administration of metformin ⁱ	←-----For the duration of the study-----→											

Table 4.2.3-1 Schedule of Treatment Period Procedures

Study Period	Treatment period											
MEDI0382 Dose level	100 µg			200 µg			300 µg					
Visit Number	V4			V5	V6	V7	V8	V9	V10	V11		
Procedure/ Study Day	-2	-1	1	2	7	8	14	15	22	27	28	29
Inpatient or Outpatient	Inpatient			Outpatient	Outpatient	Outpatient	Outpatient	Outpatient	Outpatient	Inpatient		
Administration of SC IP (MEDI0382 or placebo) ^j			X	X	X	X	X	X	X	X	X	
Uptitration of SC medication						X		X				
Capillary glucose and ketones monitoring ^k			X			X		X				
Visit requires 10-hour overnight fast the day before arrival ^l		X	X		X		X				X	
Collect Blood samples for:												
Serum chemistry (predose where applicable) ^m	X		X		X		X		X		X	
Serum amylase and lipase (predose where applicable) ⁿ	X				X		X				X	
Serum lactate	X		X		X		X		X		X	
Serum calcitonin	X										X	
pH	X		X		X		X		X		X	
Hematology (predose where applicable) ^m	X		X		X		X		X		X	
MEDI0382 PK ⁿ					X	X	X	X			X	X

Table 4.2.3-1 Schedule of Treatment Period Procedures

Study Period	Treatment period											
	100 µg			200 µg			300 µg					
Visit Number	V4			V5	V6	V7	V8	V9	V10	V11		
Procedure/ Study Day	-2	-1	1	2	7	8	14	15	22	27	28	29
Inpatient or Outpatient	Inpatient			Outpatient	Outpatient	Outpatient	Outpatient	Outpatient	Outpatient	Inpatient		
Dapagliflozin PK ⁿ		X	X		X	X	X	X			X	X
Ketones PK ^{o, r}		X	X		X	X	X	X			X	X
█████			█									█
MMTT sampling for glucose, c-peptide, glucagon, insulin, active GLP-1 ^q		X									X	
FFA (fasting)		X			X		X				X	
HbA1c	X										X	
FPG		X			X		X				X	
Collect urine for:												
Urinalysis	X						X		X	X		
Pregnancy test	X						X		X	X		
24-hour urinary glucose ^s			X								X	

Table 4.2.3-1 Schedule of Treatment Period Procedures

Study Period	Treatment period											
MEDI0382 Dose level	100 µg			200 µg		300 µg						
Visit Number	V4		V5	V6	V7	V8	V9	V10	V11			
Procedure/ Study Day	-2	-1	1	2	7	8	14	15	22	27	28	29
Inpatient or Outpatient	Inpatient		Outpatient	Outpatient	Outpatient	Outpatient	Outpatient	Outpatient	Outpatient	Inpatient		
Drug and alcohol screen ^t	X									X		
Staff review of daily ketone testing data	X				X		X		X	X		
Subjects finger-prick testing of ketones using test strips ^u	←-----For the duration of the study until 14 ± 2 days after last dose-----→											
CGM ^v	←-----From Day -1 until 28 ± 4 days after last dose -----→											
CGM sensor application/change ^w		X					X				X	
Assessment of AEs/SAEs	←-----For the duration of the study-----→											
Concomitant medications	←-----For the duration of the study-----→											

ABPM = ambulatory blood pressure monitoring; ██████████ AEs = adverse events; BP = blood pressure; CGM = continuous glucose monitoring; ECG = electrocardiogram; FFA = free fatty acid; FPG = fasting plasma glucose; GLP-1 = Glucagon-like peptide-1; HbA1c = hemoglobin A1c; HR = heart rate; IP = investigational product; MMTT = mixed meal tolerance test; PK = pharmacokinetics; RR = respiratory rate; SAEs = serious adverse events; SC = subcutaneous(ly); V = visit

- ^a The eligibility check should be based on all clinical measurements and blood tests taken during the screening visit (V1) with the exception of vital signs, urinary illicit drug, and pregnancy tests, which should be rechecked on Day -2. An abbreviated physical examination and repeat medical history should also be undertaken on Day -2 to ensure the subject is well enough to commence dosing.
- ^b On Day -1, following completion of the MMTT test, subjects are given the option to remain in the unit or return home. Discharged subjects must ensure they undergo an overnight fast for approximately 10 hours, and they will return to the clinic on Day 1.

- ^c Body weight should be measured in the morning prior to breakfast on Day 1 (predose on Day 1) and on Day 29. The subject should take off their shoes and remove bulky clothing. Calibrated scales should be used.
- ^d A single, digital ECG recording should be performed predose after the subject has rested for 10 minutes on Day 1, 7, 14, 22, and 27.
- ^e **Vital Signs schedule:** Vital signs include BP, HR, RR, and body temperature. On days when ABPM device is due to be checked, a predose set of vital signs should be performed only prior to application of the ABPM cuff. BP should be measured once at heart level in the nondominant arm where possible, and opposite to the arm where the CGM device is applied. The subject should seat and rest for 10 minutes prior to the measurement. Both lying and standing measurements should be taken.
- Day -2, 14, and 28: vital signs to be taken prior to fitting ABPM
 - Day 1: vital signs to be taken predose (-15 minutes); immediately after dosing (+ 3 minutes); 15, 30, and 60 minutes (\pm 5 minutes) postdose; and 2 hours (\pm 10 minutes) postdose
 - Day 15 and 29: vital signs to be taken once ABPM is removed
 - Day 7, 8, and 22: vital signs to be taken at no specific time point
- ^f Subjects will be fitted with the ABPM device shortly after they arrive at the clinical unit. Subjects may be involved in practice inflations. On Day -2, 14, and 28, ABPM should be applied predose. From Day 14 to Day 15, the subject will wear the monitor/cuff for approximately 24 hours (including overnight) and will remove the device at home at the end of the 24-hour period. Subjects will return the device to the clinic. On Day -1 and Day 29, the device will be removed at the clinic during the inpatient stay.
- ^g Randomization may occur any time from Day -1 to Day 1 (predose).
- ^h Normal saline will be used for SC injection administration training.
- ⁱ Metformin and dapagliflozin to be administered before investigational product administration. For PK sample collection, dapagliflozin should be administered by staff at the clinic on Days -1, 1, 7, 8, 14, 15, and 28 shortly before investigational product.
- ^j Subjects to dose at home on Day 22 and 27 prior to coming to the clinic. Investigational product will be administered in the clinic on Days 1, 2, 7, 8, 14, 15, and 28. Please refer to Investigational Medicinal Product Manual for more details.
- ^k After investigational product administration (MEDI0382 or placebo) on Day 1 (first dose) and on Days 8 and 15 (uptitration days), subjects will be monitored for safety, glucose, and ketones. Capillary blood ketones and glucose monitoring will be done with a glucometer before meal, predose, 2 hours postdose, and 4 hours postdose. The subject will be discharge 6 hours postdose.
- ^l Outside of fasting times meals/snacks and fluid intake should be standardized across each inpatient stay.
- ^m Predose labs not applicable on Day 7, 14, 22, and 28. N-B Serum chemistry will include bicarbonate measurements.
- ⁿ **PK sampling schedule:** Blood samples for PK (MEDI0382 and dapagliflozin) to be drawn as follow:
- Dapagliflozin:
 - Day -1, 7, 14, 28: Predose; 0.5, 1, and 2 hours (\pm 15 minutes) postdose; and 4, 6, 8, and 12 hours (\pm 30 minutes) postdose
 - Day 1, 8, and 15: Predose
 - Day 29: 24 hours after dosing time on Day 28

- MEDI0382
 - Day 7, 14, and 28: Predose; 0.5, 1, and 2 hours (\pm 15 minutes) postdose; and 4, 6, 8, and 12, (\pm 30 minutes) postdose
 - Day 8 and 15: Predose
 - Day 29: 24 hours after dosing time on Day 28
- **Ketone blood sampling schedule:**
 - Blood samples for ketone (β -hydroxybutyrate) PK to be drawn following an overnight fast of at least 10 hours at the following times:
 - Day -1, 7, 14, and 28: Predose; 0.5, 1, and 2 hours (\pm 15 minutes) postdose; and 4, 6, 8, and 12, (\pm 30 minutes) postdose. A standardized breakfast meal will be provided 2-hour post dose on Day 7 and 14 (see footnote “r”)
 - Additional blood samples for ketone PK to be drawn as follow:
 - Day 1, 8, and 15: Predose
 - Day 29: 24 hours after dosing time on Day 28 (\pm 30 minutes)
- [REDACTED]
- ^q **MMTT schedule:** The MMTT is conducted on Day -1 and Day 28 following a minimum 10-hour fast the day before. On Day -1, the MMTT starts 2 hours after dapagliflozin administration. On Day 28, the MMTT starts 2 hours after investigational product (MEDI0382 or placebo) and dapagliflozin administration. A blood sample for glucose metabolism panel (glucose, insulin, c-peptide, glucagon, and active GLP-1) will be taken immediately prior to the subject drinking one entire can of Ensure Plus as a standardized meal (ie, “0 minutes”). In addition, blood samples for glucose metabolism panel will be drawn at 15, 30, 45, 60, 90, 120, 180, and 240 minutes (\pm 5 minutes) after consumption of the standardized meal. Additional sampling for glucagon, insulin, c-peptide, and glucose to be taken at 6, 8, 12, and 24 hour after time 0 (\pm 30 minutes) of the standardized meal administration on Days -1 and Day 28.
- ^r **Standardized breakfast meal:** On Day 7 and 14, a standardized breakfast meal will be provided approximately 2 hours after dapagliflozin and investigational product administration. The meal will have approximately 450 kilocalories and will consist of 1 egg, 2 slices of white bread, 1 slice of Swiss cheese and 1 cup (240 ml) of orange juice (approximately 30% fat, 15% protein and 55% carbohydrates).
- ^s Twenty-four-hour urinary collection for measurements of glucose excretion to start first thing in the morning soon after waking on Day 1 and Day 28. Instruct the subject to pass urine soon after waking and flush down the toilet. Note the exact time this was done. The collection of urine will start from this time. Proceed to collect every drop of urine day and night for 24 hours and finish by passing urine the next morning at exactly the same time collection was started the day before. This urine should also be added to the bottle.
- ^t Breath alcohol testing is acceptable as an alternative to urine testing.
- ^u Subjects will be provided with a ketones monitor and strips for capillary blood ketone testing and will be instructed to test once a day (prebreakfast) and to do additional tests including glucose if they feel unwell. Subjects will be asked to record ketone values in a paper diary, which will be provided and checked by study staff.
- ^v CGM device to be fitted and worn continuously throughout the study. The sensor should be applied to the arm, taking into account which side the subject sleeps on and also which side the ABPM device will be applied. The sensor applied to the skin is single use and may not be reattached once removed.

- ^w CGM sensors last 14 days and should be changed at 14-day intervals at the same time of day (± 20 minutes) as originally applied on Day -1. For example, if the sensor is applied at 6:00 am on Day -1, it should also be applied at 6:00 am (± 20 minutes) predose on Day 14 and 28. If the sensor fails, or needs to be replaced, it should be reapplied as soon as possible.

